#### 10.6 Analysis of Secondary Endpoints

Summary statistics (n, mean, standard deviation, median, minimum and maximum) on the raw data as well as changes from baseline will be presented by timepoint for all labs shown below. If multiple labs were performed at a given timepoint, the lab results from the date the site is basing clinical care from will be used and summarized in the analysis tables. All laboratory analysis will be performed by the local labs affiliated with the hemodialysis facility.

A summary table of abnormal lab results will also be provided. All summary statistics (n, mean, standard deviation, median, minimum and maximum) will be computed relative to the lab results

that fell outside of specified ranges on the raw data. These ranges will be determined prior to data analysis.

For the PRO secondary endpoints, descriptive tests will be performed comparing last measurement (H8 or withdrawal) and first measurement (C1). Specifically, total score for EQ-5D-5L, MOS and RTQS will be compared using a 95% CI for the difference in last measurement minus first measurement. No descriptive test will be performed for the ZBI12, as it is only collected at the last study visit (H8 or withdrawal), however descriptive statistics will be displayed for the ZBI12. Similarly, the per symptom scores on the ESAS-r will be compared using a 95% CI. Finally, for TTR, the difference in rate and corresponding 95% Clopper-Pearson CI between last measurement minus first measurement for each category (0-2 hours, 2-6 hours, 6-12 hours, 12-24 hours and >24 hours) will be shown. As these endpoints are not intended for labeling, the analysis will be descriptive in nature and therefore no type I error adjustment is required.

Estimates of secondary endpoints and differences measured between the test and control periods will be reported along with their two-sided 95% confidence intervals.

Secondary safety endpoints will be analyzed in the same manner as the primary safety endpoint, as described in [Section 10.4.2](#).

Additionally, a table will be provided to show the number and percentage of the FAS subjects with at least one pre-specified AE by treatment period and overall for each dialysis treatment period (In-Center and In-Home), by MedDRA system organ class (SOC) and preferred term (PT). All AEs, all SAEs, and all device-related AEs will be summarized in a similar manner.

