- Reticulocyte count (C1, C2, C4, C6, C8, H2, H4, H6, H8, Withdrawal)
- Ultrafiltration volume (net fluid removal) (All treatments)
- Number of alarms (All treatments)
- Time to resolve alarms (All treatments)
- Types of alarms (All treatments)
- Ability to deliver prescribed treatment
- Successful training of participant and caregiver (C4, C5, C6, C7, C8)
- Attempts required to complete training successfully (C4, C5, C6, C7, C8)
- Device deficiency assessment (All treatments and Withdrawal)
- Time to recovery after dialysis (TTR) (C1, H1, H4, H8, Withdrawal)
- EQ-5D-5L (C1, H1, H8, Withdrawal)
- Medical Outcomes Study (MOS) Sleep Index (C1, H1, H8, Withdrawal)
- Renal Treatment Satisfaction Questionnaire (C1, H1, H8, Withdrawal)
- Zarit Burden Interview (ZBI-12) (H8, Withdrawal)
- Edmonton Symptom Scale (ESAS-r) (C1, H1, H8, Withdrawal)

Estimates of secondary endpoints and differences measured between the last measurement (H8 or withdrawal) and the first measurement (C1) will be reported along with their two-sided 95% confidence intervals, as applicable. For continuous endpoints, we will derive the estimate of the difference in means and its 95% CI from a paired t-test for dependent samples. For dichotomous endpoints, we will derive the estimate of the difference in proportions and its exact 95% CI based on a score statistic. In terms of the PRO secondary endpoints, the total scores for EQ-5D-5L, MOS, and RTQS, as well as the per symptom scores on the ESAS-r will be descriptively analyzed. Finally, for TTR, the difference in rate and corresponding exact 95% CI (derived from a score statistic) between last measurement minus first measurement for each category (0-2 hours, 2-6 hours, 6-12 hours, 12-24 hours and >24 hours) will be shown. As these endpoints are not intended for labeling, the analysis will be descriptive in nature and therefore no type I error adjustment is required.

The analysis of the primary and secondary endpoints will exclude the data collected from the extended treatment phase (described in section 12.2).

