13 SUMMARY OF CHANGES FROM THE PROTOCOL

The following table provides a list of changes from the protocol to the SAP, and the justification for each change. Any changes from the protocol made in the SAP will override the protocol.

Section	Description	Justification
Protocol Section 10.2.2 / SAP Section 4	Changing the number of subjects enrolled from 50 to up to 50	Clarifying that the trial will enroll up to 50 patients to obtain an evaluable sample size of 33 patients.
Protocol Section 10.3.1 / SAP Section 6.2	Updating primary analysis population to be the evaluable population rather than FAS	This decision ensures that patients will have data in both the in-clinic and in-home phases of the study which was an assumption of the power/SS calculations. The FAS does not ensure that patients will have data in both study phases.
Protocol Section 6.5 / SAP Section 7.7	Added 'unless otherwise pre-approved by sponsor' to the withdrawal if competency not achieved by C8	Sponsor will consider approving additional clinic time for participants that are competent on the SC+ but have not been deemed competent with another component of home training or whose homes were not prepared for device installation by the end of C8.
Protocol Section 10.6 / SAP Section 10.2	Changing methodology used to derive exact 95% CIs for difference in proportions from Clopper-Pearson to based on a score statistic	Clopper-Pearson is only used for exact 95% CI for a single proportion, not a difference in proportions. Exact 95% CIs based on a score statistic are more appropriate here.
Protocol Section 8.2 / SAP Section 7.7	Removing text regarding to be included in the data analysis, scheduled visits occurring after competency sign off must occur within +/- 3 days of the expected time point	This statement is not applicable to the statistical analysis due to the nature of the data collection and the frequency of visits in this study.

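### SAP 9.2 pairs the last-minus-first comparison for continuous endpoints but not for proportions, where its score interval reads as an independent-samples one

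*SAP*

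**What the plan says.** The trial follows one cohort. SAP 9.2 estimates changes from C1 to the final assessment (H8, or withdrawal if earlier), so both values come from the same people.

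For continuous endpoints the SAP takes "the estimate of the difference in means and its 95% CI from a paired t-test for dependent samples". The next sentence deals with binary ones: "For dichotomous endpoints, we will derive the estimate of the difference in proportions and its exact 95% CI based on a score statistic". For TTR, which has five mutually exclusive categories, it plans "the difference in rate and corresponding exact 95% CI (derived from a score statistic) between last measurement minus first measurement for each category". Neither sentence mentions dependence between the two measurements.

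Protocol 10.6 had planned, for TTR, "the difference in rate and corresponding 95% Clopper-Pearson CI between last measurement minus first measurement". SAP 13 replaces this because Clopper-Pearson applies to one proportion and not to a difference, and concludes: "Exact 95% CIs based on a score statistic are more appropriate here". That reason, like the matching entry in the SAP's document history, distinguishes one proportion from two. It does not distinguish independent from paired proportions.

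SAP 7.5 and 9.2 make these analyses descriptive, with no multiplicity adjustment. SAP 9.2 also says that missing secondary endpoints are not imputed.

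**The concern.** The two proportions in each difference come from the same participants, so the variance of the difference depends on how strongly a participant's two answers go together. A method for independent groups sets that dependence to zero. The SAP recognises the dependence for means, then names for proportions a method that is usually the independent-samples one.

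At stake is the reported precision of the recovery-time changes. The interval is the only inferential output planned for them, so a mis-sized one can change how a result reads. Two programmers working from the same sentence could also produce different intervals.

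**Working it through.** **Inputs from the documents.** Two-sided 95% intervals (SAP 9.2). 33 evaluable participants (SAP 4; Protocol 10.2.2), used here as 33 complete pairs. The only within-patient correlation given is 0.50, for weekly Kt/V (SAP 4); there is none for any binary endpoint. The plan states no interval width or proportion for these endpoints, so there is no figure of its own to reproduce.

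**Assumptions.** The proportions at C1 and at the final assessment, and the within-patient correlation phi. The main example takes 13/33 at C1 and 20/33 at the end, a difference of 7/33 = 0.212.

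**Formulas.** Let p1 and p2 be the two proportions and n the number of pairs.

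- Variance if unpaired: [p1(1−p1) + p2(1−p2)]/n.
- Variance if paired: the same, less 2·phi·√[p1(1−p1)p2(1−p2)]/n.
- With equal proportions, the ratio of standard errors (unpaired/paired) is therefore 1/√(1−phi).

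The intervals compared are score intervals, the type the SAP names. Each collects the values Δ at which the statistic lies within ±1.96, with nuisance proportions estimated under Δ.

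- Unpaired: (p̂2 − p̂1 − Δ) / √[p̃1(1−p̃1)/n + p̃2(1−p̃2)/n].
- Paired (Tango): (b − c − nΔ) / √[n(2q̃ + Δ(1−Δ))], where b participants enter the category, c leave it, and q̃ is the estimated probability of leaving.

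**Results, 13/33 to 20/33.** The unpaired score interval is −0.029 to 0.430 (width 0.459) whatever the correlation. Its exact version is about −0.040 to 0.445 (width about 0.485). The ratios below compare the two asymptotic score intervals, like with like.

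| Enter / leave | phi | Paired interval | Paired width | Unpaired/paired width |
|---|---|---|---|---|
| 14 / 7 | −0.24 | −0.061 to 0.453 | 0.514 | 0.89 |
| 12 / 5 | 0.02 | −0.034 to 0.433 | 0.467 | 0.98 |
| 10 / 3 | 0.27 | −0.002 to 0.412 | 0.414 | 1.11 |
| 8 / 1 | 0.52 | 0.042 to 0.389 | 0.348 | 1.32 |
| 7 / 0 | 0.65 | 0.086 to 0.378 | 0.292 | 1.57 |

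As a check on phi in the fourth row: 12 participants are in the category both times, so phi = (12/33 − 0.394×0.606)/(0.394×0.606) = (0.364 − 0.239)/0.239 = 0.52. In that row the unpaired interval includes zero and the paired one does not.

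**Other assumed tables show the same pattern.** 16/33 to 16/33: ratio 0.90 at phi −0.21 and 1.28 at 0.51. 10/33 to 16/33: 0.89 at −0.24 and 1.34 at 0.55. 3/33 to 6/33: 0.94 at −0.15 and 1.36 at 0.67.

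**Coverage.** With equal proportions, a nominal 95% unpaired interval covers approximately 2Φ(1.96/√(1−phi)) − 1: 92.6% at −0.2, 95.0% at 0, 98.1% at 0.3 and 99.4% at 0.5.

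**Which endpoints are affected.** Of the items listed in SAP 9.2, the TTR categories are the clear case. The post-dialysis blood-pressure criterion is possibly another: it is listed from C1 to H8, but SAP 10.2 also analyses it as a safety endpoint with the GEE model. Training success is recorded only at C4 to C8, so it has no C1 or H8 value.

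**The case against.** The strongest reply is that the SAP never says the interval is unpaired. Score intervals for paired proportions exist, and the preceding sentence shows that the authors knew the samples were dependent. This stands in part. A reader might infer that the plan prescribes a two-sample interval, but the text does not settle that. What it does show is that pairing is stated for means and absent for proportions, and that the reason for the change in SAP 13 concerns only one proportion versus a difference. That makes the independent-samples reading the natural one, and the one likely to be programmed.

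A reader might also infer that the intervals are bound to be too wide. The documents do not support this, because they give no correlation for any binary endpoint and the 0.50 belongs to Kt/V. Positive correlation is plausible for a broad or end category. In the middle TTR categories, however, movement between categories could bring it near or below zero.

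Nor should the simple normal-approximation figure be carried over. With equal proportions and a correlation of 0.5 it makes the unpaired interval 1/√0.5 = 1.41 times as wide, whereas the score intervals at 33 pairs give about 1.3 (1.28 and 1.32 above).

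The point that these endpoints are descriptive, with no success criterion resting on them, stands in full.

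**Conclusion.** The concern holds as a flaw in the stated method, with low impact. The last-minus-first differences in proportions are within-patient, and the interval named for them, on its natural reading, ignores that. Its width would then be wrong by an amount, and in a direction, that depends on a correlation the documents do not give. In the main example this runs from about 11% too narrow at phi −0.24 to 57% too wide at phi 0.65, and it is about right near zero. These sizes rest on 33 complete pairs and on assumed proportions and correlations.

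It would be wrong to conclude that every binary endpoint is affected or that the trial's result is at risk. The problem is confined to the TTR categories and possibly the blood-pressure criterion. Success depends on Kt/V and the adverse event rate, which are analysed by other methods.

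**What to change.** In SAP 9.2, state that differences in proportions for the TTR categories, and for any other binary endpoint measured both at C1 and at H8 or withdrawal, will have a 95% interval for paired proportions, for example Tango's score interval or Newcombe's paired method. Base it on participants with both measurements, and report how many have only one. Tango's and Newcombe's intervals are not exact, so either drop the word exact or name an exact paired version.

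Amend SAP 13 to match, giving pairing as part of the reason. Correct its cross-reference too: it places this change in SAP 10.2, but the text is in 9.2.

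The cost is a sentence or two and a different procedure call, with no new data. The one downside is that participants with a single measurement drop out of the difference; their values can still appear in the summaries by timepoint.

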10 SAFETY ANALYSES

Safety endpoints will be assessed from C1 until participant withdrawal. The analysis of the safety endpoints will exclude the data collected from the extended treatment phase. Safety endpoints will be presented using descriptive statistics and will be completed in the evaluable population.

- Vascular access complication: defined as AVF or AVG clotting during the dialysis procedure, bleeding for more than 30 minutes post-dialysis for 3 consecutive sessions, difficulty with vascular access resulting in inability to initiate or complete dialysis treatments or complications related to hemodialysis catheters (not including reduced blood flow in catheter or tissue plasminogen activator (TPA) or catheter exchange).
- Pyrogenic reaction: onset of objective chills (visible rigors) and fever (oral temperature greater than or equal to 37.5 degrees Celsius in a participant who was afebrile and who had no recorded signs or symptoms of infection before treatment.

No formal testing will be done on the rate of pre-specified AEs in accordance with NCT02460263. The estimate of the difference in rates between study phases and its 95% CI will be generated using the repeated measures GEE model as described above for the primary safety endpoint. The analysis of these pre-specified AEs will be descriptive in nature, and do not require an adjustment to be made to the type I error rate.

10.2 SECONDARY SAFETY ENDPOINTS

Secondary safety endpoints will be analyzed in the same manner as the primary safety endpoint, as described above. These shall include:

- Number of serious adverse events (SAEs) per 100 treatments occurring in the home phase of the study, compared with those occurring in the in-clinic phase
- Number of device-related AEs and SAEs per 100 treatments in the home phase of the study, compared with those occurring in the in-clinic phase
- Adverse events of special interest:
 - Individual components of the primary safety endpoint
 - Air in blood tubing that cannot be resolved through usual procedures
 - Significantly elevated venous (>250 mmHg) or negative arterial (>100 mmHg) pressures during three (3) consecutive treatments
 - Intradialytic hypotension, as defined by treatments during which hypotensive symptoms led to either lowering the ultrafiltration rate or saline administration

- Post-dialysis (within 30 minutes) systolic blood pressure <90 mmHg or systolic blood pressure >180 mmHg following two (2) consecutive treatments

Additionally, a table will be provided to show the number and percentage of the evaluable population subjects with at least one pre-specified AE by treatment period, and overall, for each dialysis treatment period (in-center and in-home), by MedDRA system organ class (SOC) and preferred term (PT). All AEs, all SAEs, and all device-related AEs will be summarized in a similar manner.

11 ADVERSE EVENTS

All adverse events (AEs) will be coded using the standardized Medical Dictionary for Regulatory Activities (MedDRA) central coding dictionary, version 24.0 or greater. All adverse event related tables and listings described below will be based on the FAS population.

11.1 ALL ADVERSE EVENTS

Summaries of incidence rates of individual AEs by System Organ Class (SOC) and Preferred Term (PT) will be presented for the FAS population. Because a patient may experience more than one AE, summaries will provide both the number of patients experiencing at least one event and the number of events within a reporting period. Percentages provided will be the percent of patients experiencing one or more adverse events. Additionally, raw adverse event rates per 100 treatments will be presented by SOC/PT for the in-clinic, transition, and in-home phases of the study to allow for fair comparison of adverse event occurrence across study periods. Due to the granularity of reporting by SOC/PT, the rates per 100 events will be raw and not computed via GEE models as in the primary safety endpoint.

A listing of all adverse events will include the subject number, AE number, start date, stop date, AE SOC and PT, severity, seriousness, action taken, outcome, and adjudication status as well as relationship to investigational device, non-investigational device, procedure, concomitant medications, pre-existing condition, intercurrent condition, intercurrent intervention, or other.

11.2 ADVERSE EVENTS LEADING TO WITHDRAWAL

A data listing of AEs leading to withdrawal in the FAS population will be provided, displaying details of the event(s) captured on the CRF.

11.3 SERIOUS ADVERSE EVENTS

Summaries of incidence rates of individual SAEs by SOC and PT will be prepared for the FAS population. Summaries will provide both the number of subjects and the number of events within a reporting period. Percentages provided will be the percent of subjects experiencing one or more serious adverse events. Additionally, raw adverse event rates per 100 treatments will be presented by SOC/PT for the in-clinic, transition, and in-home phases of the study to allow for fair comparison of adverse event occurrence across study periods. Due to the granularity of reporting by SOC/PT, the rates per 100 events will be raw and not computed via GEE models as in the primary safety endpoint.

A data listing of SAEs may also be provided, displaying details of the event(s) captured on the CRF.

11.4 DEVICE OR PROCEDURE RELATED ADVERSE EVENTS

Summaries of incidence rates of device (investigational and non-investigational) and procedure related AEs by SOC and PT will be prepared for the FAS population. Summaries will provide both the number of subjects and the number of events within a reporting period. Percentages provided will be the percent of subjects experiencing one or more device or procedure related adverse events. Additionally, raw adverse event rates per 100 treatments will be presented by SOC/PT for the in-clinic, transition, and in-home phases of the study to allow for fair comparison of adverse event occurrence across study periods. Due to the granularity of reporting by SOC/PT, the rates per 100 events will be raw and not computed via GEE models as in the primary safety endpoint.

Data listings of device and procedure related AEs may also be provided, displaying details of the event(s) captured on the CRF.

11.5 UNANTICIPATED ADVERSE EVENTS

Summaries of incidence rates of unanticipated AEs by SOC and PT will be prepared for the FAS population. Summaries will provide both the number of subjects and the number of events within a reporting period. Percentages provided will be the percent of subjects experiencing one or more unanticipated adverse events. Additionally, raw adverse event rates per 100 treatments will be presented by SOC/PT for the in-clinic, transition, and in-home phases of the study to allow for fair comparison of adverse event occurrence across study periods. Due to the granularity of reporting by SOC/PT, the rates per 100 events will be raw and not computed via GEE models as in the primary safety endpoint.

A data listing of unanticipated AEs will also be provided, displaying details of the event(s) captured on the CRF.

11.6 DEATHS

Should any subjects die during the course of the Quanta SC+ trial, relevant information will be supplied in a data listing.

12 OTHER PLANNED ANALYSES

12.1 PLANNED SUBGROUP ANALYSES

Subgroups will be performed on both co-primary effectiveness endpoints (the delivery of a mean standardized weekly Kt/V of greater than or equal to 2.1 in each of the in-center period and the in-home period), as well as the primary safety endpoint (the number of adverse events per 100 treatments occurring in the in-clinic portion of the study compared with those occurring in the home portion). The Quanta SC+ Clinical Trial is not powered for these subgroup analyses and therefore, there will be no formal hypothesis testing for the primary endpoints within subgroups. These analyses will be performed on the evaluable Population.

12.1.1 AGE

The analyses of the primary endpoints will be summarized descriptively in the following age categories: 18-50 years, 50-70 years, and 70-80 years.

12.1.2 SEX

In accordance with FDA guidance, the analyses of the primary endpoints will be summarized descriptively separately within each sex.

12.1.3 RACE

In accordance with FDA guidance, the analyses of the primary endpoints will be summarized descriptively separately within each race.

12.1.4 DRY WEIGHT AT C1

The analyses of the primary endpoints will be summarized descriptively in the following dry weight at C1 categories: 50-70 kg, 70-100 kg, and >100 kg.

12.1.5 DIABETES STATUS

The analyses of the primary endpoints will be summarized descriptively separately in patients who have diabetes and patients who do not have diabetes.

12.1.6 CARDIOVASCULAR DISEASE HISTORY

The analyses of the primary endpoints will be summarized descriptively separately in patients who have a history of cardiovascular disease and patients who do not have a history of cardiovascular disease.

12.1.7 DIALYSIS ACCESS METHOD USED FOR THE MAJORITY OF THE DURATION OF THE STUDY

The analyses of the primary endpoints will be summarized descriptively separately in patients who use the following methods for dialysis access for the majority of the duration of the study: fistula, central line, and graft.

